4.6.2 Part II: Genome-wide Gene Expression in TPAIT Patients

Small amounts of digest from the procedure used for isolating islets, and what remains in the circuit after the isolation process is complete, that would normally be discarded, will also be used for islet gene expression assessment. These collected islets will be shipped to [name] Laboratory at Stanford University School of Medicine for gene expression assessment.

For the flow cytometry, RNA isolation and RNA-sequence library preparation, islets or acinar tissues will be dispersed into single cells by enzymatic digestion and incubated. Cells will be then stained with conjugated primary antibodies and sorted, followed by cytometry data collection. The cells then will be lysed, and total RNA will be isolated. RNA quality and quantity will be measured, and RNA-Sequence libraries will be built. Sequencing RNA reads will be aligned with default parameters. Transcript counts will be obtained using a collapsed Ref-Seq reference transcriptome list.

4.7 Potential problems and alternative strategies:

The TPAIT procedure carries with it a risk of bacterial contamination from the pancreatic organ itself along with islet infusion, however CCF has one of lowest incidences (38%) than reported [60, 61]. Patients undergoing TPAIT are fully immunocompetent, and will be receiving antibiotics treatment as part of the post-operative protocols. Routine microbiological analysis will allow germ identification and prompt target therapy, if required. Patients will remain in the hospital for post-operative care (median 10 days) [1], housed in ICU after surgery. Hospitalization will be followed by outpatient daily visits for additional 5-7 days, which will allow for control of any possible event associated with the administration of HCQ. Blood glucose levels will be monitored and eventually corrected if potential hypoglycemic events associated to HCQ use should occur. Post-operatively, patients will be under continuous glucose monitoring and insulin drips and on an IV line, which will allow for a quick response to changes in glycemic levels.

[figure not shown]
Metabolic test such as arginine stimulation [62] would have been more informative than the MMTT, allowing for better control of variables such as glucagon responses. If the data support the hypothesis, in the future, a larger and more controlled phase I/II study could consider the more cumbersome, but better informative arginine stimulation test.

[name] and her clinical staff will monitor the subjects for HCQ-emergent adverse events prior to discharge and the research coordinator will follow-up by phone contact throughout the duration of the trial.

Table 2: Study Timeline

	T= -1 months	T=0 (TPAIT day)	T = +3 months	T = +6 months	T = +12 months
HCQ group (n=5)	- MMTT #1 - Start of HCQ	- Seahorse XF analyzer for isolated islets ([name] Lab) - Genomic analysis ([name] Lab)	- Discontinue HCQ	- MMTT #2	- MMTT #3
Placebo group (n=5)	- MMTT #1 - Start of placebo	- Seahorse XF analyzer for isolated islets ([name] Lab) - Genomic analysis ([name] Lab)	- Discontinue placebo	- MMTT #2	- MMTT #3

Figure 1: Study Timeline

5. Data Analysis

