Stemming from experimental and clinical transplantation data, there is general agreement that providing anti-inflammatory cover during the early post-islet infusion period can protect the graft [15, 16]. Protection of the islet graft from the initial inflammatory challenge should prevent cell loss and preserve beta cell function leading to sustained long-term insulin independence and delay of complications associated with uncontrolled hyperglycemia [17, 18]. Recent studies have proposed the use of TNF- α blockers/inhibitors to short-circuit the innate inflammation known to be detrimental to beta cell function and survival [19-25]. Etanercept, a TNF-a blocker, has been incorporated into a number of immunosuppressive protocols for islet allotransplantation which have proven successful [19, 20, 23-26]. In the multicenter Clinical Islet Transplantation (CIT) study, the use of etanercept resulted in improvement in beta cell secretory capacity of more than 40% of normal and a three-fold gain in islet engraftment efficiency [20]. When these patients were evaluated at 1 year post-transplant, they remained free of insulin use with a trend towards further improvement in beta cell secretory capacity to more than 50% of normal [20]. Even though one cannot conclude that etanercept alone was an important factor in improving the outcomes, its inclusion in the immunosuppressive regimens is believed to have made some contribution that could be relevant in preserving beta cell mass and function consequent to TNF-alpha blockade. This same mechanism of islet loss is also relevant in the autologous islet transplantation settings.

Hydroxychloroquine (HCQ) is a quinolone anti-malarial agent, FDA-approved for the treatment of autoimmune diseases. HCQ is considered the first-line agent for the treatment of rheumatoid arthritis,

systemic lupus erythematosus and sjogren syndrome [27]. The immune effects of HCQ are modulated though several mechanisms, particularly through decrease in pro-inflammatory cytokine production such as IL-1 and IL-6 and reduction of proteolysis and antigen presentation. Compared to TNF-a blockers, HCQ is administered orally, is relatively inexpensive, and has excellent tolerability with minimal side effect profile.

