3.5 Benefits and risks

Hydroxychloroquine is considered to be among the safest antirheumatic medications with the potential for any serious adverse event being extremely rare [53]. Gastrointestinal symptoms are the most common side effects, nausea being the most common. The relative safety of HCQ has resulted in no regular laboratory testing required to monitor for toxicities. Monitoring for adverse events is clinical. Retinopathy is the most notable complication of HCQ, though any serious ophthalmologic toxicity is rarely seen with regular follow up. The risk of retinopathy increases with higher dosages and longer durations of therapy. In a study of 2,361 patients on HCQ for at least 5 years, the prevalence of retinal toxicity was less than 2 percent during the first 10 years of therapy in patients treated with 4.0 to 5.0 mg/kg of real body weight [54]. The current 2016 revised recommendations of the American Academy of Ophthalmology recommend that all patients undergo a baseline eye examination before or within a year of beginning the treatment with HCQ [55]. Given that that the likelihood of HCQ-induced retinopathy is rare with shortterm use (i.e. 4 months in this pilot study), no baseline ophthalmological evaluation will be mandated. However, patients with preexisting retinopathy will be disqualified from enrollment.

Table 1: Inclusion/Exclusion Criteria

Inclusion criteria for TPAIT [1, 56]	Exclusion criteria for TPAIT [1, 56]	
--------------------------------------	--------------------------------------	--

Inclusion criteria for HCQ phase	Exclusion criteria for HCQ phase		
Acceptance for TPAIT at CC Age range 18-65	Manufacturer's product label-contraindicated use of HCQ History of retinopathy Actual weight at enrollment <40 Kg Inclusion/exclusion criteria for TPAIT unmet		

4. Research Procedures

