4.5 Exploratory mechanistic studies

All subjects will undergo a MMTT to assess islet cell function at 6 and 12 months following TPAIT (in addition to MMTT pre-surgery performed as standard of care, and whose results will be used for prerandomization in this pilot). Baseline metabolic tests obtained too early after surgery may not be indicative of islet function, due to insulin supporting therapy administered for several weeks after transplantation. Also, compelling data indicate that stabilization of islet function may require up to 1 year to occur. Blood glucose and C-peptide serum levels will be measured in peripheral blood samples immediately prior and subsequent to MMTT. Laboratory tests will be measured in CCF hospital laboratory.

The research coordinator will contact the subjects at 3, 6 and 12 months for interview on the course of follow up and will assist in scheduling the 6 and 12-month appointments for MMTT.

4.6 Innovation:

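### Section 4.7 words adverse event monitoring by attribution to HCQ and leaves the term undefined, so recording rests on a causal call that can differ by arm and weakens the placebo comparison

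*Combined protocol and SAP*

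**What the plan says.** Three statements in section 4.7 describe how adverse events are watched for, and all three refer to the active drug:

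- In hospital, clinical staff "will monitor the subjects for HCQ-emergent adverse events prior to discharge".
- The daily outpatient visits after discharge are described as something "which will allow for control of any possible event associated with the administration of HCQ".
- On glucose: "Blood glucose levels will be monitored and eventually corrected if potential hypoglycemic events associated to HCQ use should occur".

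The sentence on in-hospital monitoring ends with "the research coordinator will follow-up by phone contact throughout the duration of the trial", and states no scope of events for those calls. Section 4.5 adds scheduled contacts: "The research coordinator will contact the subjects at 3, 6 and 12 months for interview on the course of follow up". Section 3.5 says that monitoring is clinical and names the effects to expect: "Gastrointestinal symptoms are the most common side effects, nausea being the most common".

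Section 4.3 unblinds the surgeons and the research coordinator. Sections 3.2 and 4.4 give the placebo arm (n=5) the same schedule as the HCQ arm (n=5). Study drug starts 30 days before surgery and continues for 3 months after it. Sections 5.1 and 5.2 list no safety measure, and section 5.5 gives no safety analysis. Section 6 (Adverse Events and Data Monitoring Committee) appears only as a heading in the text available.

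**The concern.** A placebo arm lets events be counted by arm without anyone deciding what caused each one. Wording that records events by their link to HCQ puts that decision first, and here the decision is hard to make. Nausea after pancreatectomy and low glucose on an insulin drip look the same whether or not the subject takes HCQ. The coordinator who makes the follow-up calls knows the allocation, so the same complaint may be logged in one arm and put down to surgery in the other.

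At stake is whether the pilot's event counts can be compared between arms at all. The background section says the data will inform a later trial of dosage and timing. Its stated aim there is beta cell function, but tolerability by arm is an obvious by-product of a placebo-controlled pilot, and the readable plan does not secure it.

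**Working it through.** **The plan's own figure.** The documents give no safety figure. The 5 per arm comes from the efficacy calculation in section 5.5: one-sided two-sample t-test, difference 0.12, SD 0.07, alpha 0.05, 75% power. It reproduces: exact power at 5 per arm is 79.6%, and 5 is the smallest size reaching 75%. This does not bear on safety beyond fixing the sample size.

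**The wording, point by point.**

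1. *Scope.* All three monitoring statements in 4.7 name HCQ. None says study drug or placebo, and HCQ-emergent is not defined. No readable passage says that all events are recorded in both arms, gives a method for judging causality, or plans a summary by arm.
2. *Overlap.* The effects named are nausea (3.5) and hypoglycemia (4.7). Section 4.7 puts post-operative patients on insulin drips. That both events also occur without HCQ in this setting is a clinical inference; the documents give no background rate for either.
3. *Who decides.* The coordinator is unblinded (4.3) and carries follow-up after discharge (4.7 and 4.5).
4. *The pre-operative month.* It is 30 days of roughly 4 months on drug, about a quarter, and the only on-drug period without surgical background. Staff monitoring is described only up to discharge, and the scheduled interviews begin at month 3. The phone contact may cover this month, but the text does not say so.

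**How attribution can distort the count (illustration, assumed figures).** Suppose 3 of 5 subjects in each arm have nausea, so the true difference is 0. If all events are recorded, the table shows 3/5 v 3/5. If someone who knows the arm records only what is ascribed to HCQ, it can show anything from 3/5 v 0/5 (all ascribed in the HCQ arm) to 0/5 v 0/5 (all ascribed to surgery). The apparent difference then runs from 0 to 60 percentage points by recording alone.

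**What 5 v 5 could show with full recording.**

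- 3/5 v 0/5: one-sided Fisher p = C(5,3)/C(10,3) = 10/120 = 0.083; two-sided 0.167.
- 4/5 v 0/5: one-sided p = C(5,4)/C(10,4) = 5/210 = 0.024; two-sided 0.048.
- 0/5 events: one-sided 95% upper bound = 1 − 0.05^(1/5) = 0.45.
- Chance of at least one event in an arm: 1 − 0.95^5 = 0.23 at an assumed 5% rate; 1 − 0.90^5 = 0.41 at an assumed 10% rate.

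**The case against.** The strongest reply is that the text never restricts collection to HCQ-caused events in the HCQ arm. It says the subjects, without naming an arm. Emergent can mean onset during treatment, as in treatment-emergent, and would then cover both arms. Section 4.3 says only the surgeons and the coordinator are unblinded, so other ward staff, not knowing who takes HCQ, would have to apply the rule to everyone. (Section 3.1 also calls the trial open label, so this is not fully settled.) The phone calls and the interviews at 3, 6 and 12 months carry no event restriction, the registry's safety fields are not listed, and section 6 may have lost its text.

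Most of this stands, and it rules out a stronger reading. A reader might infer that collection is limited to HCQ-related events, that the rule cannot apply to placebo subjects, and that no safety comparison is possible. The documents support none of these: the comparison is unspecified and open to bias, not excluded.

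A reader might also infer that infection is set aside because "Patients undergoing TPAIT are fully immunocompetent". The same sentence goes on to antibiotic treatment, and routine microbiology is described next; immunocompetence is never given as a reason not to track infection by arm. Nor does the 38% in 4.7 show that infections are near certain in both arms. It is a contamination rate, and the documents give no rate at which contamination leads to clinical infection.

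It can also be said that full recording would not settle whether HCQ adds events at this sample size. That is true, but it is no reason to let recording depend on attribution. What the reply does not remove is the undefined term, the three statements tied to HCQ, and the unblinded coordinator.

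**Conclusion.** The point holds as one of wording and bias. Section 4.7 frames monitoring by attribution to HCQ, does not define the term, and leaves post-discharge follow-up with someone who knows the allocation. Taken literally, this makes recording depend on a causal call that can differ by arm, which weakens the placebo comparison.

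The size of the bias cannot be computed, because the documents give no background event rates and no causality method; the 0 to 60 point range above is an illustration only. The conclusion assumes that the named HCQ effects overlap with post-surgical events, and that section 6 does not already prescribe all-event recording. If section 6 does, what remains is a mismatch of wording to be reconciled. If treatment-emergent was meant, the change only states it. Even with full recording, 5 v 5 is descriptive. The change should be made because it is cheap and better than the rule as worded; the efficacy analysis is not affected.

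**What to change.** - In section 4.7, replace the HCQ-emergent wording with all adverse events regardless of suspected cause. Record them identically in both arms, from first dose (so including the 30-day pre-operative period) through the phone follow-up already planned for the whole trial.
- Record relatedness to study drug as a separate field, judged by staff blinded to allocation and not by the coordinator.
- In section 5, add a descriptive tabulation of events by arm, and state that 5 v 5 supports no inferential safety conclusion.
- Reconcile all of this with section 6, whose text is not readable here.

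The cost is a few sentences, some REDCap fields and one table. The main burden is more events to log, most of them surgical. Since the coordinator stays unblinded, elicitation by phone keeps some risk of bias; recording everything reduces that risk but does not remove it.

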5.1 Study endpoints

- 5.1.1 Primary endpoints:
 - Quotient of MMTT stimulated (90min) C-peptide/glucose/IEQ/Kg at 6 and 12 months after TPAIT.

Rationale for the proposed endpoint: MMTT is a common metabolic test used to assess the insulin and C-peptide response to a mixed meal challenge. It triggers physiologic pathways to induce maximal insulin and C-peptide secretion. It is simple to conduct, and the outcome is widely believed to represent beta cell insulin secretion capacity. In recipients of islet allografts, the ratio of MMTT C-peptide/glucose at 90min correlates with the islet mass infused and it proves a valuable indicator of islet function. Whereas IVGTT

is also broadly utilized to assess islet function, our preference has been given to a test that shows correlation with predicted islet yield (used in a pre-randomization step) and infused islet mass.

5.1.2 Secondary endpoints:

- Stimulated C-peptide area under the curve (AUC) in response to MMTT at 6 and 12 months after TPAIT.
- Stimulated glucose AUC in response to MMTT at 6 and 12 months after TPAIT.
- Stimulated C-peptide and glucose levels in response to MMTT at 6 and 12 month after TPAIT.

5.1.3 Innovative endpoints:

5.1.3.1 Part I: Mitochondrial Function and Metabolic Outcomes in TPAIT

Oxygen consumption rate (OCP) and extracellular acidification rate (ECAR) of isolated islets' mitochondria in subjects receiving HCQ and placebo.

5.1.3.2 Part II: Genome-wide Gene Expression in TPAIT Patients

Differential gene expression calls will be done on isolated islets. These will be compared to appropriate control gene expression sets [52].

5.2 Study outcomes:

5.2.1 Primary outcomes:

- Increased quotient of stimulated C-peptide/glucose level normalized for IEQ/Kg infused in response to MMTT at 12 months in the HCQ-treated compared to placebo arm.

5.2.2 Secondary outcomes:

- Higher C-peptide AUC in response to MMTT 12 months in the HCQ-treated compared to placebo arm.
- Higher ratio of C-peptide AUC to glucose AUC in response to MMTT at 12 months in the HCQ-treated compared to placebo arm.

5.2.3 Innovative outcomes:

- Lower rates of oxygen consumption within isolated islets from CP patients compared to commercial controls
- Higher rates of oxygen consumption within isolated islets of HCQ-treated subjects compared to placebo.
- Full RNA sequence library for isolated islets from CP patients

5.3 Data collection:

The clinical data will be collected under auto islet registry stored in REDCap. All data in the Islet Isolation Laboratory at the Institute of Cellular Therapeutics, Allegheny Health Network and [name] Laboratory of the Cleveland Clinic Lerner Research Institute will be de-identified and collected into Microsoft Excel as medium, then transferred to REDCap by the investigators. All investigators will have received proper HIPPA training.

5.4 Data access and confidentiality:

All data will be collected either directly into REDCap or indirectly through Microsoft Excel on CCF Desktop computer as medium. The data will contain no personal health identifier (PHI) when it is being shared with investigators outside of the CCF. A study ID will be assigned to each subject. The deidentified clinical data will be shared for the purpose of manuscript construction under the standard user data agreement from the CCF IRB Committee. All investigators will have received proper HIPPA training.

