2.1.2 Part II: Genome-wide Gene Expression in TPAIT Patients

Previous investigations have identified pathways that regulate human beta-cell proliferation, function and maturation [48-51]. The genes regulating beta-cell proliferation and function may change dramatically with various factors, such as age [52]. Little is known about the gene signatures for islets from an inflammatory environment, particularly long-term CP patients, whose pancreata have been altered by the disease over time. The gene expression may influence the islet engraftment, survival, function and proliferation and impact the metabolic outcomes in islet transplantation.

We **hypothesize** that the gene expression signature plays a significant role in the clinical outcomes in TPAIT in patients with CP. Specifically, this study would help to determine:

- 1. Whether there is heterogeneity in the autoislet gene expression profiles prepared for TP-AIT
- 2. How the heterogeneity in the gene expression profiles is related to clinical outcomes of AIT

3. Study Design

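### Part II sequences islets from both randomised arms but specifies no HCQ-versus-placebo expression contrast and does not use arm as a factor in any of its analyses

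*Combined protocol and SAP*

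**What the plan says.** Sections 4.2 and 4.4 randomise subjects 1:1 before pancreatectomy and start study drug 30 days before transplant, with placebo on the same schedule. Table 2 then puts "Genomic analysis ([name] Lab") in the transplant-day cell of both the HCQ row and the placebo row.

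For Part II, section 5.1.3.2 says "Differential gene expression calls will be done on isolated islets" and continues "These will be compared to appropriate control gene expression sets [52"]. The matching outcome in section 5.2.3 is "Full RNA sequence library for isolated islets from CP patients". Section 2.1.2 sets two further questions: whether the autoislet profiles are heterogeneous, and how that heterogeneity relates to clinical outcome. None of these statements mentions treatment arm.

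For Part I, the endpoint in section 5.1.3.1 is defined "in subjects receiving HCQ and placebo", and section 5.2.3 lists "Higher rates of oxygen consumption within isolated islets of HCQ-treated subjects compared to placebo". The statistical section, 5.5, deals only with the C-peptide/glucose quotient.

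**The concern.** The trial's hypothesis is that HCQ protects islets by attenuating inflammation, and the background attributes its action to, among other things, "decrease in pro-inflammatory cytokine production such as IL-1 and IL-6". The plan lists no cytokine endpoint. Islet RNA is the planned assay closest to that mechanism, and it is collected in both arms under random allocation. Yet the plan does not say that the arms will be compared on it.

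Two consequences follow for the analyses that are planned. First, the comparison with control sets is not randomised, and section 2.1.2 itself warns that relevant genes "may change dramatically with various factors, such as age [52"]. If the patients are treated as one group, an HCQ effect in half of them is added to whatever disease or age difference is present. Second, HCQ is expected to change the metabolic outcome and may change expression. An association pooled over arms could then reflect treatment alone.

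At stake is how far the mechanistic results can be interpreted in a pilot meant to inform a later trial. The primary endpoint does not depend on this.

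**Working it through.** **1. Part I and Part II side by side.**

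| | Part I (respiration) | Part II (expression) |
|---|---|---|
| Islets taken | Transplant day, both arms | Transplant day, both arms |
| HCQ hypothesis | Yes (2.1.1) | None (2.1.2) |
| Arm in endpoint | Yes (5.1.3.1) | No (5.1.3.2) |
| Arm in outcome | Yes (5.2.3) | No (5.2.3) |
| Other comparisons | Commercial control islets; metabolic outcome | Control sets; heterogeneity; clinical outcome |

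**2. The plan's own sample size.** Inputs from section 5.5: difference 0.12, SD 0.07, one-sided alpha 0.05, 5 per arm. Standardised difference d = 0.12/0.07 = 1.71. Noncentrality = d × √(n/2) = 1.714 × √2.5 = 2.71, with 8 df and critical t = 1.860. Power is 79.6%, and 5 is the smallest n that reaches 75%. All nine cells of Table 3 reproduce. The plan gives no such figure for expression.

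**3. What an arm contrast could detect.** Same noncentral-t method, 5 v 5, 8 df, two-sided alpha 0.05 (critical t = 2.306):
- 75% power: d = 1.90 SD; 80% power: d = 2.02 SD.
- With one df spent on predicted-yield group (7 df): 1.94 and 2.07 SD.
- At the one-sided 0.05 used for the primary endpoint (8 df): 1.61 and 1.72 SD.

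**4. Genome-wide search.** The documents give no gene count, so 10,000 to 20,000 is assumed. With two-sided Bonferroni control at 0.05, 80% power needs 8.07 to 8.82 SD. At d = 1.71 the power per gene is about 0.10% to 0.05%. The smallest two-sided permutation p-value with 5 v 5 is 2/252 = 0.0079, far above 0.05/10,000 = 0.000005.

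**5. How omitting arm distorts the planned analyses.**
- Control sets: with 5 of 10 patients exposed, pooled difference = (untreated patients − controls) + 0.5 × (HCQ effect). An HCQ effect of 1.9 SD would shift it by 0.95 SD.
- Expression and outcome: suppose HCQ shifts expression by d and outcome by e within-arm SDs, and the two are unrelated within arm. With 1:1 allocation, pooled correlation = (de/4) / √[(1 + d²/4)(1 + e²/4)]. For illustration take d = e = 1.71, the effect assumed for the primary endpoint: d²/4 = 0.735, so r = 0.735/1.735 = 0.42. The association would come from treatment alone.

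**6. Chance imbalance between arms.** The difference in mean age, in SD units, has standard error √(2/5) = 0.632. P(gap above 0.5 SD) = 2 × [1 − Φ(0.5/0.632)] = 0.43 under a normal approximation.

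**The case against.** The strongest reply is that this is a choice of scope. Section 2.1.1 states an HCQ hypothesis for Part I; section 2.1.2 states a disease-signature and outcome hypothesis for Part II and no drug hypothesis. In a 10-patient pilot, leaving out a further contrast is defensible. That stands as an argument against making the contrast a main objective. It does not answer step 5, because the questions Part II does ask are themselves affected by arm.

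A reader might infer more than the documents support:
- That the libraries go unused, or that an arm contrast is ruled out. Section 2.1.2 plans two within-cohort analyses of them, and the wording on expression calls is open enough to allow an arm contrast. The contrast is unspecified, not excluded.
- That expression is the only randomised measurement on the graft islets. Part I compares respiration by arm.
- That the arm contrast would be free of age or batch problems. Allocation makes it unconfounded by design, but a mean-age gap above 0.5 SD would arise by chance about 43% of the time, and batches could also line up with arm.
- That the control sets are known to be badly matched or sequenced elsewhere. The text calls them appropriate and cites a source; their external origin and any batch difference are inferences.
- That an IL-1/IL-6 score is the obvious lead analysis. The background puts the cytokine peak within 6 hours after infusion and names infiltrating immune cells as a source. Section 4.6.2 uses pre-infusion digest, sorted into populations it does not name. Such a score could miss the relevant cells.

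Usable RNA from all 10 subjects is also not assured, since the material is left-over digest.

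**Conclusion.** The concern holds as an omission in specification. Part II prespecifies no HCQ-versus-placebo expression contrast and uses arm in none of its analyses, although both arms are sequenced after about a month of randomised study drug and Part I does compare the arms. As written, half of any HCQ effect passes into a pooled patient-versus-control difference, and the expression-outcome association can be produced by treatment.

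An arm contrast would be exploratory only: about 1.9 to 2.0 SD for one prespecified score, assuming 10 usable samples, equal variances and approximate normality, and no realistic genome-wide power. The 0.95 SD shift and the 0.42 correlation illustrate assumed effects and are not predictions. The documents do not support saying that the data would be wasted or that the planned comparisons are invalid. This is a low-cost improvement to an exploratory part of the trial.

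**What to change.** In sections 5.1.3.2 and 5.2.3:
- Add an exploratory HCQ-versus-placebo differential-expression contrast. Report either effect estimates with false-discovery control or a short gene set named in advance and suited to the cell populations actually sorted.
- Include arm as a factor in the expression-outcome analysis.
- Show the comparison with control sets separately by arm, and label it descriptive.
- State that 5 v 5 detects only about 1.9 to 2.0 SD for one prespecified score (two-sided 0.05, 75% to 80% power) and cannot support genome-wide inference.

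Optionally, where the sequencing laboratory finds it practical, process or at least record library batches so that batch and arm do not coincide. Recruitment is expected to take 12 months, so holding samples for balanced batches would change that laboratory's workflow; recording batch would not.

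The cost is a few lines of text and a little extra analysis of data already being generated. Section 8 puts the RNA analysis at no charge to the study. The downside is one more result that can only be exploratory.
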